## 13. Data Analysis

**Preliminary Data:** Amplitude titration has been completed with non-human primates but has yet to be completed with human subjects and modern ECT parameters. *I/Ebrain* bridges the gap from amplitude titration in non-human primates to changes in hippocampal neuroplasticity in human subjects. *I/Ebrain* is the ratio of electrode current strength (*I*) to the E-field strength in the brain (*Ebrain*) . *Ebrain* will be computed as the 90th percentile of E-field magnitudes from all voxels in the brain, serving as an estimate of the peak induced field strength while avoiding the influence of tissue boundary effects that could bias the absolute maximum E-field values. For example, one subject with 800 mA extracranial amplitude produces 0.8 V/cm 90th percentile E-field strength. The ratio would be 1000 mA/V/cm, which means 1000 mA produces 1 V/cm. A second subject with the same 800 mA extracranial amplitude produces 1.2 V/cm 90th percentile E-field. The ratio would be 667 mA/V/cm, which means 667 mA produces 1 V/cm. *Ebrain* is a whole brain E-field metric as the location of seizure duration is unknown.

The relationship from amplitude titration to hippocampal neuroplasticity is illustrated here (**Figure 4**). First, we demonstrate that amplitude-titrated seizure threshold increases with *I/Ebrain* in non-human primates (**4A**). Second, we demonstrate that increased *I/Ebrain* is related to decreased hippocampal E-field (current dependent metric, input current set here at 1 mA) (**4B1**). For fixed amplitude ECT, *I/Ebrain* is inversely related to hippocampal volume change. *Ehippo* is the 95th percentile E-field in the hippocampus and will be an exploratory measure of this investigation. However, the focus on amplitude titrated seizure threshold requires *Ebrain*, a whole brain E-field metric, as the regions involved in seizure induction are unknown. Third, we demonstrate that increased hippocampal E-field is related to increased hippocampal neuroplasticity across all amplitudes (600, 700, and 800 mA) and electrode placements (RUL and BT) (**4B2**). This relationship is a replication of the GEMRIC data (Figure 2) with our U01 data. Fourth, we

performed an analysis of a subset of our data comparing  $I/E_{brain}$  with hippocampal volumetric change with 800 mA subjects (**4B3**).

[figure not shown]

Figure 4: The multi-step relationship from amplitude titration to hippocampal neuroplasticity.

A) Non-human primate data.  $I_{\text{Electrode}}/E_{\text{brain}}$  (see description in Preliminary Data). Increased  $I/E_{\text{brain}}$  is related to increased amplitude required for seizure titration ( $r = 0.84$ ,  $p < 0.0001$ ).

B1) U01 data, all subjects.  $I_{\text{Electrode}}/E_{\text{brain}}$  is inversely related to hippocampal E-field magnitude with an amplitude intensity of 1 mA, which is baseline for E-field modeling ( $r = -0.79$ , Cohen's  $f^2 = 1.66$ ).

B2) U01 data, all subjects. Electrode placement (RUL and BT) and amplitude (600, 700, 800 mA) are based on the subject's last treatment. Right hippocampal E-field magnitude is directly related to right hippocampal neuroplasticity for all amplitude strengths (600, 700, and 800 mA) and electrode placements (right unilateral and bitemporal) ( $r = 0.49$ , Cohen's  $f^2 = 0.33$ ).

B3) U01 data, subjects from the 800 mA arm.  $I_{\text{Electrode}}/E_{\text{brain}}$  is inversely related to right hippocampal neuroplasticity for 800 mA subjects ( $r = -0.62$ , Cohen's  $f^2 = 0.62$ ).

C1) Hypothesized relationship. Increased  $I_{\text{Electrode}}/E_{\text{brain}}$  is related to increased amplitude required for seizure titration (verification of non-human primate data depicted in 4A).

C2) Hypothesized relationship (Go-No-go). The ratio of fixed amplitude ECT (800 mA) relative to amplitude seizure titration will be associated with right hippocampal neuroplasticity.

Summary, interpretation, and alternatives: To illustrate the application of these principles, we use our preliminary data (**4B3**) and hypothesized relationships (**4C1** and **4C2**). We also use the example of 2% hippocampal growth as optimal for antidepressant response (optimal hippocampal growth will be determined with a receiver operating curve (ROC) curve predicting Inventory of Depressive Symptomatology (IDS-C30) total score decrease during the R61). With traditional 800 mA amplitude, the 2% volume increase is related to an  $I/E_{brain}$  of  $\sim 625$  mA/V/cm (**4B3**) and fixed/amplitude ratio of  $\sim 2.7$  (**4C2**). Subject #1 (orange star) has a low (250 mA) seizure threshold (ST) (**4C1**),  $I/E_{brain}$  of  $\sim 600$  mA/V/cm (**4C2**) and a fixed/amplitude ratio of  $800/250 = 3.2$  (**4C2**). Subject #1 will need an input current of  $2.7 \times ST = 2.7 \times 250$  mA = 675 mA for 2% hippocampal volume increase. In contrast, Subject #2 (green star) has a high (350 mA) seizure threshold,  $I/E_{brain}$  of  $\sim 750$  mA/V/cm and a fixed/amplitude ratio of  $800/350 = 2.3$ . In order to achieve the 2% volumetric increase, Subject #2 will require an increased X/amplitude ratio from 2.3 to 2.7. Subject #2 will need an input current of  $2.7 \times ST = 2.7 \times 350$  mA = 950 mA for 2% hippocampal volume increase. We stress that the fixed/amplitude ratio  $\sim 2.7$  for 2% hippocampal volume increase is conceptual and will be determined during the R61.

H1: Amplitude seizure titration will have a positive correlation with  $I/E_{brain}$  (**Figure 4C1**). This is a replication of the data from the non-human primate data. The relationship between  $I/E_{brain}$  and amplitude titration is the foundation for the rationale of this proposal.

Statistical approach for H1: Let  $(x, y)_i$  be the observed vector of response for  $I/E_{brain}$  and seizure threshold for each patient,  $I = 1, \dots, n$ . The Pearson correlation will be calculated and the standard one-sided t-test with 2 degrees-of-freedom will be conducted for testing whether the correlation is positive,  $H_0: \rho > 0$ .

Power calculation for H1: The observed correlation in Figure 4A is  $r = 0.84$  for non-human primates and we expect that the more conservative Cohen's "large" effect size  $r = 0.5$  is a realistic lower bound for our population, thus a sample size of  $n = 29$  provides 80% power at a  $0.05 / 2 = 0.025$  significance level.

Go/No-Go criterion (H2): The ratio of amplitude titration to fixed amplitude ECT will demonstrate a linear relationship with treatment-responsive changes in hippocampal neuroplasticity. This relationship will determine the "neuroplasticity multiplier" to bridge from amplitude titration to hippocampal neuroplasticity.

Statistical approach for H2: We will perform a multiple regression accounting for covariates age and sex,  $\%Vol_{Scaled}$  Change =  $\beta_0 + \beta_1 M + \beta_2$  age +  $\beta_3$  sex, where the effect size is  $f^2 = R^2 / (1 - R^2)$ , with  $R^2$  the coefficient of determination with the interpretation of "the proportion of variance explained" in the response by the model over the grand mean. We will test whether the regression model explains a significant proportion of variance in the response, expecting that the key relationship is between  $\%Vol_{Scaled}$  change and multiplier  $M$ .

Power calculation for H2: The relationship we are expecting in Figure 4C2 is derived from Figures 4B3 and 4C1. Starting with Figure 4B3, the relationship of  $I/E_{brain}$  on  $\%Vol_{Scaled}$  change has a correlation of  $r = -0.62$  with an effect size  $f^2 = 0.624$ , well above the Cohen's "large" effect size of  $f^2 = 0.35$ . Figure 4C1 is Figure A with the axes reversed, thus the

correlation is  $r = 0.84$ . We will assume that the relationship between %VolScaled Change and multiplier M will remain consistent with Cohen's "large" effect size. Then a sample size of  $n = 36$  provides 80% power at a 0.05 significance level.

The Holm Procedure, a multi-step step-down procedure useful for endpoints with any degree of correlation, will adjust the two hypotheses below for multiple comparison. For our situation, this means H1 is tested at the  $0.05 / 2$  significance level and H2 is tested at  $0.05 / (2-1) = 0.05$ ; however, H2 is tested only if H1 is significant.

The Go/No-Go criterion is set to "Go" if we can reject the null hypothesis that  $H_0: \beta_1=0$  at a 0.05 significance level in the model specified in Hypothesis H2, that is, that multiplier M remains a significant predictor of %VolScaled Change after adjusting for age and sex.

## **14. Provisions to Monitor the Data to Ensure the Safety of Subjects**

Data safety and monitoring will be carried out to ensure and maintain the scientific integrity of this project and to protect the safety of our participants. Safety monitoring is the process during the study that involves review of accumulated outcome data for groups of subjects to determine if any of the procedures practiced should be altered or stopped. Ultimately, the PI ([name]) will be responsible for monitoring the safety of the study and complying with the reporting requirements. An independent Data Safety and Monitoring Board (DSMB) will review the study data on a biennial basis with the PI to ensure participant safety (re: subject recruitment at 20 subjects/year, DSMB meetings every ~ 10 participants). The Data Safety and Monitoring Board will include [name] [name] (DSMB Chair/Dept. of Neurology), [name] (Dept. of Anesthesiology), and [name] (PI at Mind Research Network). The board members have no conflicts of interest or roles with the current project. Drs. [name] and [name] have experience participating in ECT-related DSMB, and [name] has extensive clinical experience with ECT. Continuous, close monitoring of participant safety will include prompt and frequent reporting of safety data (i.e., adverse/serious adverse events) to the DMSB, the University of New Mexico Health Sciences Center Institutional Review Board (UNMHSC IRB) and/or appropriate NIH staff with oversight responsibility. The focus of adverse event reporting will be the first treatment of the ECT series, which is the only experimental treatment for this phase of the project. The first treatment will be amplitude titration (as opposed to the more traditional titration based on pulse number or frequency). The amplitude titration will result in reduced amplitudes (hypothesized range will be between 250 and 550mA, traditional ECT is conducted at 800mA). Adverse events may include expected side effects related to ECT: headaches, nausea (from anesthesia), and muscle aches (from anesthesia). Unexpected side effects (to be determined) will also be reviewed with the DSMB. In addition, relevant published data related to the study protocol will also be presented to the DSMB. The DSMB will evaluate the adverse effects of the first treatment in relation to the expected side effects related to a traditional ECT series. The PI will provide a summary of the safe conduct of the study to NIH and FDA on an annual basis as part of the progress report. All AEs occurring during the course of the study will be collected, documented, and reported to the UNMHSC IRB. The review of data may result in early termination of the study, amendment to the protocol, or changes to

the data collection plan or study forms if it appears that there are adverse events directly related to the first (experimental) treatment. Significant adverse events directly related to the experimental treatment (amplitude titration, treatment#1) such as hospitalization and death will warrant suspension or termination of research. Should the protocol, data collection plans or study forms be amended as a result of data review, the IRB will be notified and the amendment approved prior to study amendment implementation. In addition, the participants will be notified of any significant new findings that develop during the course of research that may affect their wish to continue participation in the study.

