Subjects (n = 40) will receive amplitude titrated seizure threshold during the first treatment with RUL . The Soterix 4X1 High Definition ECT Multi-channel Stimulation Interface (“Soterix Interface”) is a passive amplitude reducer for the MECTA 5000Q. The Soterix Interface reduces the amplitude range to 200 mA and permits 50 mA incremental dosing throughout the 200 to 900 mA dosing range. Pulse width (1.0 ms), pulse train duration (8 s), and frequency (20 Hz, 320 pulses) will be fixed for amplitude titration. Subjects will receive stimulations starting with 200 mA with 50 mA increases until seizure activity is initiated. Clinical judgement will define seizure adequacy based on duration and morphology. In addition, subjects will receive amplitude titrated motor threshold after administration of general anesthesia during the second ECT treatment (exploratory aim, see “Motor Titration” below). After amplitude titrated seizure threshold, subsequent treatments will be completed with RUL fixed 800 mA with the same pulse width (1.0 ms) and pulse number (8 s, 20 Hz, and 320 pulses). If the subject fails to demonstrate improvement at V2 (< 25% reduction from baseline IDS-C30 total score), the subject will then receive traditional BT for the remainder of the ECT series.

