## **33. Drugs or Devices (see section 9. Resources Available)**

The research involves an investigational device. The Mecta Spectrum 5000Q paired with Soterix Medical 4X1 HD-ECT Multi-Channel Stimulation Interface is intended to reduce ECT current amplitude for amplitude-seizure titration and has received approval from the Food and Drug Administration (refer to “supporting documents”). Digitimer DS8R Biphasic Constant Current Stimulator will be used for motor titration during the second treatment.

These devices will be solely handled and operated by credentialed UNM ECT providers at the UNMH Post Anesthesia Care Unit (inpatient) or UNM Outpatient Surgical Imaging Services (outpatient).

Additionally, the research proposal will use DC-EEG device. The SMARTING (<https://mbraintrain.com/smarting/>) is a small, mobile EEG device that incorporates motion sensors that detect head and body movements. This EEG system will include a 24-channel recording cap. EEG data will be wirelessly recorded to mobile app and is capable of measuring low frequency EEG (< 0.01) pertinent for this proposal.

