*The risks of low-amplitude seizure and motor titration will be minimal relative to the traditional (higher) ECT amplitudes. The experimental portion of this protocol is relevant only to the first treatment with the remaining treatments completed at the traditional 800 mA amplitudes. Subjects will also receive more comprehensive clinical and neuropsychological assessments by participating in this research protocol relative to routine clinical care.*

7. If this study involves a health or behavioral intervention, describe why the relation of the anticipated benefit to the risk of the research is at least as favorable to the subjects as that presented by alternative procedures.

*This investigation proposes use amplitude titration relative to the traditional pulse-number based titration and fixed amplitude ECT. This difference is only relevant to the first treatment. The remaining treatments will be completed with traditional 800 mA ECT.*

8. Describe your plans for monitoring the well-being of subjects including any plans to withdraw subjects from the research if they appear to be unduly distressed.

*Subjects that appear to be distressed will be encouraged to withdraw from the study protocol. If subjects appear to be unduly distressed, the study PI will withdraw these subjects from the protocol. Data regarding subject drop-out will be documented and presented to the DSMB.*

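### Section 14's adverse event focus and stopping conditions name only treatment 1 and leave out the research motor titration at treatment 2

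*Protocol*

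**What the plan says.** Section 14 of the Protocol sets the scope of safety monitoring around the first treatment in four places.

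- **Adverse event focus:** "The focus of adverse event reporting will be the first treatment of the ECT series, which is the only experimental treatment for this phase".
- **DSMB evaluation:** "The DSMB will evaluate the adverse effects of the first treatment in relation to the expected side effects related to a traditional ECT series".
- **Permissive action clause:** data review may lead to early termination, a protocol amendment, or changes to data collection or forms, "if it appears that there are adverse events directly related to the first (experimental) treatment".
- **Mandatory action clause:** "Significant adverse events directly related to the experimental treatment (amplitude titration, treatment#1) such as hospitalization and death will warrant suspension or termination of research".

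The same section opens with a wider purpose. Accumulated data are reviewed "to determine if any of the procedures practiced should be altered or stopped".

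Other sections describe a second research procedure. Section 3 (repeated in Section 12) says that "subjects will receive amplitude titrated motor threshold after administration of general anesthesia during the second ECT treatment" and labels this an exploratory aim. Section 33 adds: "Digitimer DS8R Biphasic Constant Current Stimulator will be used for motor titration during the second treatment". In Section 44, item A.6 justifies the risk of the study as follows: "The risks of low-amplitude seizure and motor titration will be minimal relative to the traditional (higher) ECT amplitudes". The next sentence of A.6 then says that the experimental part concerns the first treatment only.

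**The concern.** Motor titration is done for research, under general anesthesia, with its own stimulator, at a session that Section 14 does not cover in its specific clauses. The mandatory clause leaves no room to read it in, because its parenthesis names both the procedure and the treatment number.

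At stake is participant protection. For one research procedure, a hospitalization or death judged directly related to it brings a written duty to suspend or end the study. For the other, the same event leaves the decision to discretion. Nothing in the protocol explains the difference. A.6 calls the risk of both titrations minimal in the same sentence, so low risk cannot be the reason that only one of them has a stopping condition.

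**Working it through.** No sample size, power or error rate is involved, so the check sets the texts side by side.

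**Step 1. Research procedures in the protocol.** Two are delivered during the ECT series with stimulation equipment:

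| | Amplitude seizure titration | Motor titration |
|---|---|---|
| When | Treatment 1 (Sections 3, 12) | Treatment 2 (Sections 3, 12, 33) |
| Purpose | Supplies the seizure threshold for H1 and H2 | Exploratory aim |
| Equipment | ECT device with the amplitude-reducing interface | Separate constant-current stimulator |
| Risk described in Section 44 A.6 | Yes, minimal | Yes, minimal |

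**Step 2. Coverage by each Section 14 provision.**

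| Provision | Seizure titration | Motor titration |
|---|---|---|
| Adverse events collected and reported to the IRB | Yes | Yes |
| Prompt adverse event reporting to DSMB, IRB and/or NIH staff | Yes | Yes |
| Unexpected side effects reviewed with the DSMB | Yes | Yes |
| General remit to alter or stop procedures | Yes | Yes |
| Stated focus of adverse event reporting | Yes | No |
| Stated DSMB evaluation of adverse effects | Yes | No |
| Stated condition for amending or terminating | Yes | No |
| Mandatory suspension or termination condition | Yes | No |

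The general provisions cover both procedures. All four specific ones cover only the first.

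**Step 3. One event, two origins.** Suppose a subject is hospitalized and the event is judged directly related to a titration. If it was the seizure titration, the mandatory clause applies. If it was the motor titration, the event is not related to treatment 1, so the mandatory clause does not apply, nor does the permissive one. The event is still reported, and the DSMB may still act under its opening remit, but no written condition is met.

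**Step 4. Internal consistency of A.6.** One sentence counts motor titration among the risks to be justified. The next confines the experimental part to the first treatment. Motor titration takes place at the second, so the second sentence does not fit the first.

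**Extent.** The design plans 40 subjects and gives each one a motor titration, so all 40 planned procedures fall outside the mandatory condition, while all 40 planned seizure titrations fall inside it. This counts exposure, not harm.

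**The case against.** The strongest reply is that safety oversight is already broad. All adverse events in the study are documented and go to the IRB. Adverse and serious adverse events are reported promptly to the DSMB, the IRB and/or NIH staff. Unexpected side effects go to the DSMB whatever the treatment number, and NIH and FDA receive an annual safety summary. For individual subjects, Section 44 requires withdrawal on loss of decisional capacity (A.3) or undue distress (A.8). All of this stands. It means that event capture is intact and that nothing forbids the DSMB from acting. It does not supply the missing study-level condition.

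A second reply is that Section 14 speaks of the only experimental *treatment*, whereas motor titration is a threshold measurement made before a conventional 800 mA treatment. That is a fair reading, and the sentence need not be called false. The scope of the clauses built on it is still too narrow.

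A third is that Sections 3 and 12 point to a fuller description of motor titration that is not in the text available. It may hold further safety provisions. Its absence is not counted as an error here, and it would not alter Section 14's own wording.

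A reader might infer more than the documents support:

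- **That the later fixed 320-pulse sessions also need a stopping condition.** The protocol does contrast fixed with traditionally variable pulse number, but 800 mA is the traditional amplitude and nothing shows that 320 pulses carries added risk.
- **That cognitive harm is outside monitoring.** Section 14 provides for review of accumulated outcome data, and the cognitive tests are among the study's assessments. The list of expected side effects is only illustrative, and the capacity rule in A.3 covers part of the concern.
- **That A.7 is wrong as well.** It says that a difference concerns only the first treatment, but the difference it has defined is the method of titration and amplitude dosing. As a statement about that, it is accurate.
- **That a chance of such an event can be stated.** The documents give no event rate for motor titration, so any probability would rest on an invented input.

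**Conclusion.** The point holds in a narrow form. Section 14 states rules whose scope omits one of the study's two titration procedures, and A.6 is inconsistent about the same procedure. The consequence is specific: a significant event caused by motor titration would not meet the written mandatory suspension condition, although the DSMB could still suspend the study under its general remit.

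This rests on two readings: that motor titration is research and not care, which its label as an exploratory aim supports, and that the mandatory clause means what its parenthesis says. It does not rest on any claim that motor titration is dangerous, or that adverse events would go unreported.

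The matter concerns safety monitoring, not the analysis. H1, H2 and the Go/No-Go criterion are untouched. The change is optional and a cheap improvement.

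**What to change.** 1. **Section 14, adverse event focus.** Replace the reference to the first treatment as the sole experimental one with: *the research procedures: amplitude seizure titration (treatment 1) and motor titration (treatment 2)*.
2. **Section 14, DSMB evaluation sentence.** Use the same wording in place of the first treatment.
3. **Section 14, both action clauses.** Use it again in the amend-or-terminate condition, and in place of the parenthesis in the mandatory suspension condition.
4. **Section 44 A.6.** Correct the sentence that limits the experimental part to the first treatment, for example: *The experimental procedures are seizure titration at the first treatment and motor titration at the second.* Leave A.7 as it stands.

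The cost is one wording amendment through the IRB. No data, visits or subjects are added. The wider condition could pause the study after a serious event at motor titration, which is the same consequence the protocol already accepts for seizure titration.
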